2. STUDY OBJECTIVES

2.1 Primary objective(s)

The study will include patients with advanced neuroendocrine neoplasms in four different cohorts with the following primary endpoints:

Primary endpoint for cohorts 1, 2 and 3:

Nine-months clinical benefit rate (CBR) by Response Evaluation Criteria In Solid Tumors (RECIST 1.1), which is defined as the percentage of patients achieving complete response (CR), partial response (PR), or stable disease (SD) at month 9 after durvalumab plus tremelimumab was started.

Primary endpoint for cohort 4:

Nine-months overall survival rate, which is defined as the percentage of patients alive at month 9 after durvalumab plus tremelimumab was started.

Clinical Study Protocol
 Drug Substance DURVALUMAB/TREMELIMUMAB
 Study Number ESR 15-11561-61-DUNE
 EudraCT Nº: 2016-002858-20
 Edition Number: 5.0 dated on June 09th, 2021

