5. For patients included in cohort 4: WHO classification G3 (Ki67 $\geq 20\%$ or mitotic count > 20 mitoses $\times 10$ HPF) gastroenteropancreatic neuroendocrine carcinomas (NEC) or liver metastases of G3 NEC of unknown primary site.
6. Subjects must have evidence of measurable disease meeting the following criteria:
 - a) In case of more than one target lesion, it should be identified at least 1 lesion of ≥ 1.0 cm in the longest diameter for a non lymph node, or ≥ 1.5 cm in the short-axis diameter for a lymph node, which is serially measurable according to RECIST 1.1 using computerized tomography/magnetic resonance imaging (CT/MRI). If there is only one target lesion and it is a non-lymph node, it should have a longest diameter of ≥ 1.5 cm.

Clinical Study Protocol
 Drug Substance DURVALUMAB/TREMELIMUMAB
 Study Number ESR 15-11561-61-DUNE
 EudraCT Nº: 2016-002858-20
 Edition Number: 5.0 dated on June 09th, 2021

- b) Lesions that have had external beam radiotherapy (EBRT) or loco-regional therapies such as radiofrequency (RF) ablation or liver embolization must show evidence of progressive disease based on RECIST 1.1 to be deemed a target lesion.
- c) Subjects must show evidence of disease progression by radiologic image techniques within 12 months (an additional month will be allowed to accommodate actual dates of performance of scans, i.e., within \leq 13 months) prior to signing informed consent, according to RECIST 1.1.

7. Eastern Cooperative Oncology Group (ECOG) performance status of 0 or 1.

8. Life expectancy of at least 12 weeks.

9. Adequate normal organ and marrow function as defined below:

- Haemoglobin \geq 9.0 g/dL.
- Absolute neutrophil count (ANC) \geq 1.5 \times 10⁹/L (\geq 1500 per mm³).
- Platelet count \geq 100 \times 10⁹/L (\geq 100,000 per mm³).

10. Serum bilirubin \leq 1.5 \times institutional upper limit of normal (ULN). This will not apply to subjects with confirmed Gilbert's syndrome (persistent or recurrent hyperbilirubinemia that is predominantly unconjugated in the absence of hemolysis or hepatic pathology), who will be allowed only in consultation with their physician.

11. AST (SGOT)/ALT (SGPT) \leq 2.5 \times institutional upper limit of normal unless liver metastases are present, in which case it must be \leq 5x ULN.

12. Serum creatinine CL>40 mL/min by the Cockcroft-Gault formula (Cockcroft and Gault 1976) or by 24-hour urine collection for determination of creatinine clearance:

Males:

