11. STATISTICAL METHODS AND SAMPLE SIZE DETERMINATION

11.1. Description of analysis sets

The statistical analyses described in this section will be performed as further outlined in the Statistical Analysis Plan, which will be included in the clinical study report for this protocol.

Analysis Sets

The analysis sets will be defined as follows:

- **Full Analysis Set** will include all allocated subjects. This will be primary analysis set for the efficacy endpoints.
- **Per Protocol Analysis Set** will include those subjects who were allocated and received at least one dose of the assigned study drug and had no major protocol deviations. The subjects will complete both baseline and at least one post-baseline tumor assessments (week 12).
- **Safety Analysis Set** will include all subjects who were allocated and received at least one dose of the study drug and had at least one post-baseline safety evaluation (week 12). This will be the analysis set for all safety evaluations.
- **Pharmacodynamic Analysis Set**: All the subjects who have received at least one dose of study drug and have evaluable pharmacodynamic data.

Demographic and other baseline characteristics

Demographic and other baseline characteristics will be summarized and listed. For continuous demographic/baseline variables including age, weight, and vital signs, results will be summarized and presented as n, number of not available data (NA), mean, standard deviation, median, and minimum and maximum values. For categorical variables such as race/ethnicity, the number and percentage of subjects will be used.

Prior and concomitant medications

Concomitant medications will be assigned an 11-digit code using the World Health Organization Drug Dictionary (WHO DD) drug codes. Concomitant medications will be further coded to the appropriate Anatomical-Therapeutic-Chemical (ATC) code indicating therapeutic classification. Prior and concomitant medications will be summarized and listed by drug and drug class.

Efficacy Analyses

All efficacy analyses will be based primarily on the Full Analysis Set and secondarily on the Per

Clinical Study Protocol
 Drug Substance DURVALUMAB/TREMELIMUMAB
 Study Number ESR 15-11561-61-DUNE
 EudraCT Nº: 2016-002858-20
 Edition Number: 5.0 dated on June 09th, 2021

Protocol Analysis Set.

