Data cut-off for the primary study analysis will happen following after the last patient included in the study has performed the first tumor evaluation (week 12 after first dose of study drug). The following tumor evaluations will take place every 12 weeks until documentation of disease progression or start of another anticancer therapy.

Analysis of primary efficacy variable

The analysis of clinical benefit rate and overall survival rate will be performed independently for each study cohort when the last patient included in the corresponding cohort of the study will arrived to 9 months after inclusion in the study or have progressed. The primary objective of the study will be based on the investigator assessment.

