- CT/MRI of chest/abdomen/pelvis and other areas of known disease at screening plus any areas of newly suspected disease should be performed every 8 weeks for the first 48 weeks and then every 12 weeks until confirmed PD (Date of assessment and status (PD or not PD)).

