2 EFFICACY ANALYSES

All efficacy analyses will be based primarily on the Full Analysis Set and secondarily on the Per Protocol Analysis Set.

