2.1.2 Primary efficacy analyses in the Per Protocol Analysis Set

The primary endpoint for cohort 1, 2 and 3 is the CBR, nevertheless the result for all the cohorts will be shown below:

Table 96 Clinical benefit rate (investigator assessment) at 9 months in the Per Protocol Analysis Set

	Cohort 1	Cohort 2	Cohort 3	Cohort 4	Total
CBR at 9 months	n (% , CI 95%)				
Yes (CR, PR, SD)					
No (PD)					
Total	n (100%)				

The primary endpoint for cohort 4 is 9-months overall survival rate, which is defined as the percentage of patients alive at 9 months after durvalumab plus tremelimumab was started, nevertheless the result for all the cohorts will be shown in the following table.

Table 97 Overall survival rate at 9 months in the Per Protocol Analysis Set

	Cohort 1	Cohort 2	Cohort 3	Cohort 4	Total
Overall survival rate at 9 months	n (% , CI 95%)				
Alive					
Death					
Total	n (100%)				

Concordance between investigator assessment and independent central radiology review will be analyzed using Cohen's Kappa. Although no significant differences are expected, a sensitivity analysis for the primary efficacy analysis will be performed using as response variable independent

Statistical Analysis Plan
 Drug Substance DURVALUMAB/TREMELIMUMAB
 Study Number ESR 15-11561-DUNE
 EudraCT Nº: 2016-002858-20
 Version Number: 1.1 dated on 30/NOV/2017
 central radiology assessment.

Table 98 Agreement in CBR by Cohen's kappa coefficient in the Per Protocol Analysis Set

	Cohort 1	Cohort 2	Cohort 3	Cohort 4	Total
CBR at 9 months	Kappa k				
Investigator assessment vs. Independent review					

9-months clinical benefit rate (CBR) by Response Evaluation Criteria In Solid Tumors (RECIST version 1.1), according to independent central radiology.

Table 99 Clinical benefit rate (independent central radiology) at 9 months in the Per Protocol Analysis Set

	Cohort 1	Cohort 2	Cohort 3	Cohort 4	Total
CBR at 9 months	n (% , CI 95%)				
Yes (CR, PR, SD)					
No (PD)					
Total	n (100%)				

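### The per-protocol set requires a scan after baseline, so deaths before the first scan drop out and the per-protocol 9-month survival rate is biased upward, most clearly in cohort 4

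*Protocol*

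**What the plan says.** The Full Analysis Set "will include all allocated subjects. This will be primary analysis set for the efficacy endpoints" (Protocol 11.1). The per-protocol set takes patients with one or more doses and no major deviation, and adds: "The subjects will complete both baseline and at least one post-baseline tumor assessments (week 12". SAP 3.7.1 and SAP Table 3 repeat this condition.

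On timing, Protocol 11.1 sets the data cut-off for when the last patient "has performed the first tumor evaluation (week 12 after first dose of study drug", which places the first on-study scan at week 12. SAP 3.5 has a different schedule, in which imaging "should be performed every 8 weeks for the first 48 weeks and then every 12 weeks until confirmed PD".

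On use, SAP section 2 states: "All efficacy analyses will be based primarily on the Full Analysis Set and secondarily on the Per Protocol Analysis Set". SAP 2.1.2 plans Table 97, "Overall survival rate at 9 months in the Per Protocol Analysis Set", for all cohorts. For cohort 4 this is the primary endpoint, "which is defined as the percentage of patients alive at month 9 after durvalumab plus tremelimumab was started" (Protocol 2.1). SAP 2.2.3 (Table 109) and 2.2.4 (Table 111) report PFS and OS on the same set. Table numbers here are those in the body of the SAP.

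Neither document moves the time origin to the first scan, keeps early deaths in the per-protocol set as failures, or adjusts the 13% reference for this set.

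**The concern.** A per-protocol set is meant to select on adherence. This one also selects on an outcome, because a fully adherent patient who dies in week 6 cannot enter it. Survival status needs no scan, so for this endpoint the condition does nothing except remove failures.

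Cohort 4 is where it matters most. These are grade 3 neoplasms that have progressed on first-line platinum chemotherapy, with a planning reference of 13% alive at 9 months, so some deaths before week 12 are to be expected. Readers treat a per-protocol result as a check on the primary one. If it is tilted in one direction, agreement with the Full Analysis Set tells them little, and a more favourable figure may only reflect who was left out. Protocol 11.2 says strategic decisions about immune therapy in these tumours will follow from the results.

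**Working it through.** **Inputs.** From Protocol 11.3: cohort 4 reference 13% alive at 9 months, expected increase 10 points (target 23%), margin 5 points, one-sided 5%, 33 enrolled. From Protocol 11.1: first scan at week 12. I take the 33 as given; whether it follows from the stated design inputs is a separate question. The plan has no figure of its own for 12-week survival or for the size of the per-protocol set, so there is none to reproduce.

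**Direction.** Let S be the proportion alive at the first scan. Everyone alive at 9 months was alive at the first scan. If every patient alive then is scanned,

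per-protocol 9-month rate = S(9 months) / S.

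This exceeds S(9 months) whenever anyone dies before the scan. No hazard model is needed.

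**Size.** S has to be assumed.

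- Constant hazard: 12 weeks = 12 × 7 / 30.44 = 2.76 months. S = 0.13^(2.76/9) = 0.13^0.307 = 0.535. The rate is 0.13 / 0.535 = 24.3%, and about 33 × 0.465 = 15 patients leave the set.
- Rising hazard (Weibull shape 1.5, 2, 3): S = 0.707, 0.825, 0.943, giving rates of 18.4%, 15.7% and 13.8%.
- First scan at week 8, constant hazard: S = 0.659, giving 0.13 / 0.659 = 19.7%.

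**Rejection probability.** For a per-protocol size N, let c(N) be the smallest count with P(X ≥ c | N, p0) ≤ 0.05. Then average over N:

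P(reject) = Σ Bin(N; 33, S) × P(X ≥ c(N) | N, 0.13/S), with the true 9-month rate at 13%.

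The test is run against p0 = 13% and against p0 = 18% (13% plus the 5-point margin), because the documents do not say which value the binomial test uses.

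| Alive at week 12 | Expected set size | Per-protocol rate | Reject vs 13% | Reject vs 18% |
|---|---|---|---|---|
| 100% | 33 | 13.0% | 2.2% | 0.2% |
| 95% | 31.4 | 13.7% | 4.9% | 0.6% |
| 90% | 29.7 | 14.4% | 5.7% | 0.8% |
| 80% | 26.4 | 16.3% | 8.6% | 1.6% |
| 70% | 23.1 | 18.6% | 14.1% | 3.5% |
| 60% | 19.8 | 21.7% | 22.2% | 7.2% |
| 53.5% (constant hazard) | 17.7 | 24.3% | 28.9% | 11.3% |

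With a week-8 first scan and constant hazard, rejection against 13% is 17.1%.

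Part of the step from 2.2% to 4.9% is the coarseness of the exact test: at n = 33 the cut is 9 and the size 2.2%, while at n = 30 the cut is 8 and the size 3.4%. Rejection exceeds the nominal 5% in every row from 90% alive downward.

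**The case against.** The strongest reply is that this touches only a secondary analysis and that the large numbers sit at one end of the range.

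- **Role.** The Full Analysis Set is primary and, as defined, has no scan condition. The binomial test is assigned to the primary efficacy analysis; Table 97 shows counts, percentages and confidence intervals. This stands, and it limits the seriousness of the point. (Protocol 11.2 puts a one-scan condition on dropouts in the primary endpoint analysis; that is a related but separate matter.)
- **Size.** Eligibility asks for "Life expectancy of at least 12 weeks" and ECOG 0 or 1, which makes the milder rows more plausible. That criterion is a judgement at entry, however, and does not rule out early deaths.
- **Week 12.** The wording asks for one or more scans after baseline, so an earlier scan might qualify, as would a week-8 scan under SAP 3.5. This shrinks the effect but leaves it in place.
- **Transparency.** SAP Table 4 lists each excluded patient with the reason, and Full Analysis Set results appear in the same format. A careful reader could see how many early deaths were removed, but the per-protocol estimate would still be biased.
- **Response endpoints.** Requiring a scan is defensible for response. For clinical benefit rate and PFS, patients whose early progression was seen on a scan stay in the set; the bias there comes from death or deterioration without a scan, and it is not quantified here.

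A reader might infer that the cohort 4 per-protocol result would look positive with no drug effect, or could rescue a negative primary result. The documents do not support either reading. Even under constant hazard the test against 13% fails to reject about 71% of the time, and no rule lets the per-protocol result override the Full Analysis Set.

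**Conclusion.** The definition is wrong as written for survival endpoints. Removing patients who die before the first scan can only raise the per-protocol 9-month survival rate, and nothing in either document corrects for it. The direction of this effect rests on no model; other exclusions, such as major deviations or patients alive but not scanned, could move the estimate either way.

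The size cannot be fixed from the documents. On a true 13% in cohort 4 it runs from +0.7 points (95% alive at week 12) to +11.3 points (constant hazard). That the per-protocol rate passes the 23% target with no drug effect holds only at the constant-hazard end. These figures assume that everyone alive at the first scan is scanned and that no one is excluded for another reason. Only cohort 4 survival has been quantified.

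The point should be corrected, but it does not invalidate the primary analysis.

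**What to change.** In Protocol 11.1, SAP 3.7.1 and SAP Table 3, delete the tumour-assessment condition from the per-protocol definition. Keep one or more doses and no major protocol deviation, and state that death before the first scan counts as failure.

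If a set restricted to scanned patients is wanted for response endpoints, define it separately as response-evaluable and do not use it for 9-month survival, OS or PFS.

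Reconcile the 12-weekly scan schedule in the protocol with the 8-weekly one in SAP 3.5 and SAP Table 1, so that the timing of the first scan is unambiguous.

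The definition change is one sentence in three places, with no new data and no change to the sample size. The cost is that the per-protocol estimates become less favourable.

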- ECOG will be performed at the Screening and Baseline Visits and at every subsequent treatment visit thereafter.
- Assessments will include vital signs (supine BP, HR, RR, and body temperature), weight, and

Clinical Study Protocol
 Drug Substance DURVALUMAB/TREMELIMUMAB
 Study Number ESR 15-11561-61-DUNE
 EudraCT Nº: 2016-002858-20
 Edition Number: 5.0 dated on June 09th, 2021

height. Height will be measured at the Screening Visit only. Elevated BP ($\geq 140/90$ mmHg) should be confirmed by 3 measurements (at least 5 minutes apart). If systolic BP is ≥ 160 mmHg or diastolic BP ≥ 100 mmHg, BP should be confirmed by repeat measurements after an hour. Subjects will have their blood pressure and pulse measured before, during, and after the infusion at the following times (based on a 60-minute infusion):

- At the beginning of the infusion (at 0 minutes)
- At 30 minutes during the infusion (± 5 minutes)
- At the end of the infusion (at 60 minutes ± 5 minutes)
- In the 1 hour observation period post-infusion: 30 and 60 minutes after the infusion (ie, 90 and 120 minutes from the start of the infusion) (± 5 minutes) – for the first infusion only and then for subsequent infusions as clinically indicated

If the infusion takes longer than 60 minutes, then blood pressure and pulse measurements should follow the principles as described above or more frequently if clinically indicated. According to section 8.2.4.

- e) Required if screening physical examination was performed > 7 days prior C1D1.
- f) A comprehensive physical examination (including a neurological examination) will be performed at the Screening or Baseline Visit, on each visit of the Treatment phase, and at the off-treatment assessment. A symptom-directed physical examination will be performed on Cycle 1/Day 1 and at any time during the study, as clinically indicated.
- g) Single 12-lead ECG. Subjects must be in the recumbent position for a period of 5 minutes prior to the ECG.
- h) Assessments scheduled may be performed within 72 hours prior to the visit. Assessments during follow up are made every 8-12 weeks, according to investigator's criteria. According to section 8.2.5.
- i) Free T3 and free T4 will only be measured if TSH is abnormal. They should also be measured if there is clinical suspicion of an adverse event related to the endocrine system. Assessments during follow up are made every 8-12 weeks, according to investigator's criteria.

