3.3 Study Oversight for Safety Evaluation

A subject may elect to discontinue study drug at any time for safety, medical, or personal reasons. Patients who choose to discontinue study drug prior to disease progression will be followed in the post study treatment follow up period and continue to undergo regularly scheduled disease assessment until documentation of disease progression or start of an alternative anticancer treatment. All subjects who discontinue study drug will be followed for overall survival and all post progression cancer treatments administered will be recorded. Subjects may at any time withdraw consent for further study participation. No further data will be collected on subjects once consent has been withdrawn. The investigator will promptly explain to the subject involved that the study drug will be discontinued for that subject and provide appropriate medical treatment and other necessary measures for the subject. A subject who has ceased to return for visits will be followed up by mail, phone, or other means as much as possible to gather information such as the reason for failure to return and the status of treatment compliance, presence or absence of adverse events, and clinical courses of signs and symptoms, and the information will be recorded in the CRF.

Subjects who discontinue early from the study or treatment will be discontinued for 1 of these primary reasons: adverse event(s), lost to follow-up, subject choice, progressive disease, or administrative/other. In addition to the primary reason, the subject may have indicated 1 or more of these reasons as secondary reasons for discontinuation. Study disposition information will be collected on the appropriate CRF. A subject removed from the study for any reason may not be replaced.

Safety will be assessed by monitoring and recording all AEs including all CTCAE grades (for both increasing and decreasing severity) and serious adverse events (SAEs); regular monitoring of hematology, clinical chemistry, and urine values; physical examinations; and regular measurement of vital signs, and electrocardiograms (ECGs) as detailed in the schedule of visits and procedures.

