8.1.2 Treatment Phase

Procedures to be conducted during the treatment phase of the study are presented in the Schedule of Assessments. Screening procedures performed within 72 hours of Cycle 1 Day 1 (C1D1) do not need to be repeated on C1D1.

Efforts should be made to conduct study visits on the day scheduled (\pm 1 day). Clinical laboratory

Clinical Study Protocol
 Drug Substance DURVALUMAB/TREMELIMUMAB
 Study Number ESR 15-11561-61-DUNE
 EudraCT N°: 2016-002858-20
 Edition Number: 5.0 dated on June 09th, 2021

assessments may be conducted anytime within 72 hours prior to the scheduled visit, unless otherwise specified in the Schedule of Visits and Procedures. Results of the laboratory assessments should be reviewed always prior each cycle dose administration. Whenever possible, subjects should be evaluated at approximately the same time of the day (e.g., morning or afternoon) at each visit, and reasonable efforts should be made to conduct all evaluations in the same test order at each visit.

Tumor assessments should be performed at time points indicated in the Schedule of Visits and Procedures.

Cycle 1/Day 1

- Obtain vital signs (resting BP, HR, RR, body temperature) and weight.
- Physical examination is not mandatory if performed at baseline (day -1) however a symptom-directed physical examination will be performed on Cycle 1/Day 1 and at any time during the study, as clinically indicated.
- Administer study drug:
 - Record all concomitant medication use.
 - Record any AEs or SAEs.

Cycle 1/Day 15

- Obtain vital signs (resting BP, HR, RR, body temperature) and weight.
- Evaluate ECOG performance status.
- Perform a comprehensive physical examination (including a neurological evaluation). A symptom-directed physical examination will be performed at any time during the study, as clinically indicated.
- Collect blood samples for biochemistry and hematology analyses (see Tables 4 and 5), including TSH, fT3 and fT4.
- Urinalysis (see Table 6)
- Record all concomitant medication use.
- Record any AEs or SAEs.

Cycle 2/Day 1

- Evaluate ECOG performance status.
- Obtain vital signs (supine BP, HR, RR, body temperature) and weight.
- Perform a comprehensive physical examination (including a neurological evaluation). A symptom-directed physical examination will be performed at any time during the study, as clinically indicated.
- Collect blood samples for biochemistry and hematology analyses (see Tables 4 and 5), including TSH, fT3 and fT4.

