8.2.4 Vital signs

Vital signs (blood pressure [BP], pulse, temperature, and respiration rate) will be evaluated according to the assessment schedules.

On infusion days, patients receiving durvalumab + tremelimumab treatment will be monitored during and after infusion of IP as presented in the bulleted list below.

Clinical Study Protocol
 Drug Substance DURVALUMAB/TREMELIMUMAB
 Study Number ESR 15-11561-61-DUNE
 EudraCT Nº: 2016-002858-20
 Edition Number: 5.0 dated on June 09th, 2021

Supine BP will be measured using a semi-automatic BP recording device with an appropriate cuff size, after the patient has rested for at least 5 minutes. BP and pulse will be collected from patients receiving durvalumab + tremelimumab treatment before, during, and after each infusion at the following times (based on a 60-minute infusion):

Prior to the beginning of the infusion (measured once from approximately 30 minutes before up to 0 minutes [ie, the beginning of the infusion]).

Approximately 30 minutes during the infusion (**halfway** through infusion).

At the end of the infusion (approximately 60 minutes ±5 minutes).

A 1-hour observation period is required after the first infusion of durvalumab and tremelimumab.

If no clinically significant infusion reactions are observed during or after the first cycle, subsequent infusion observation periods can be at the Investigator's discretion (suggested 30 minutes after each durvalumab and tremelimumab infusion).

If the infusion takes longer than 60 minutes, then BP and pulse measurements should follow the principles as described above or be taken more frequently if clinically indicated. The date and time of collection and measurement will be recorded on the appropriate eCRF. Additional monitoring with assessment of vital signs is at the discretion of the Investigator per standard clinical practice or as clinically indicated.

Body weight is also recorded along with vital signs.

Situations in which vital signs results should be reported as AEs are described in Section 10.3. A complete physical examination will be performed and will include an assessment of the following (as clinically indicated): general appearance, respiratory, cardiovascular, abdominal, skin, head and neck (including ears, eyes, nose and throat), lymph nodes, thyroid, musculoskeletal (including spine and extremities), genital/rectal, and neurological systems and at screening only, height.

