11.2. Methods of statistical analyses

Strategic decisions about future development of immune therapy in neuroendocrine tumors will be available after the results of this trial.

Summary tables (descriptive statistics and frequency tables) will be provided for all baseline variables, efficacy variables, and safety variables, as appropriate. Continuous variables will be summarized with descriptive statistics (mean, standard deviation, range, and median). Ninety-five (95) percent confidence intervals (95% CI) may also be presented, as appropriate. Frequency counts and percentage of subjects within each category will be provided for categorical data.

The primary efficacy analysis will be performed using the binomial test procedure. Missing data will be treated using statistical multiple random imputation.

Secondary endpoints will be summarized with descriptive statistics. Continuous variables will be summarized with n, mean, standard deviation, and range, frequency counts and percentage of subjects within each category will be provided for categorical data. Multivariate regression models will be used to study relations between explanatory variables and primary endpoint. Survival analysis will be performed to analyze PFS, Kaplan-Meier curves will be presented and possible comparisons will be tested using the log-rank test or the Cox proportional hazard model for multivariate analysis, hazard ratios (HR) and their 95% confidence interval (CI95%) will be provided. Patients with lost of follow-up or treatment discontinuation will be included in the final analysis of primary endpoint if they have at least one tumor evaluation and considered as censored data for survival endpoints.

R software version 3.2.1 will be used for all analysis.

Safety Analyses

Safety analyses will be based on the Safety Analysis Set. All safety analyses will be summarized separately by cohort. Adverse events and serious adverse events, laboratory test results, physical examination findings and vital signs, and their changes from baseline will be summarized using descriptive statistics. Abnormal values will be flagged.

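### The Safety Analysis Set carries an ambiguous week-12 condition that, if applied, removes dosed patients who die, withdraw consent or are lost before week 12 from every safety table

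*Protocol*

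**What the plan says.** Protocol 11.1 and SAP 3.7.1 admit to the Safety Analysis Set allocated patients who received at least one dose and who "had at least one post-baseline safety evaluation (week 12). This will be the analysis set for all safety evaluations". SAP Table 3 repeats the condition. Protocol 11.2 and SAP 3.7.3 then add: "Safety analyses will be based on the Safety Analysis Set". No other safety population is defined, and nothing explains the parenthesis.

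Elsewhere in the same sections, week 12 belongs to tumor imaging. The data cut-off paragraph of Protocol 11.1 waits until the last patient "has performed the first tumor evaluation (week 12 after first dose of study drug)", and the Per Protocol bullet directly above the safety bullet attaches the same tag to its tumor assessment.

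Safety observation starts much earlier than week 12:

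- Footnote d of the protocol's schedule of assessments: "Subjects will have their blood pressure and pulse measured before, during, and after the infusion at the following times".
- Protocol 8.2.4: "A 1-hour observation period is required after the first infusion of durvalumab and tremelimumab".
- Protocol 8.1.2 lists "Record any AEs or SAEs" at Cycle 1 Day 1 and again at Cycle 1 Day 15, where a physical examination and laboratory tests are also scheduled.

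**The concern.** A safety population should be fixed by exposure. Here membership may also depend on what happens after exposure, namely surviving and remaining in the study to week 12. Cycles last 4 weeks, so week 12 is the start of cycle 4, and the window before it holds the first three of the four combination cycles. A toxic death in that window is the event a safety table most needs to show, and under the strict reading it would be absent from all toxicity rates.

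Safety is a stated secondary objective. SAP Tables 3 and 4 require a yes/no membership decision and a listed reason for each exclusion, so someone must choose a reading. The plan leaves that choice open until the data have been seen.

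**Working it through.** The plan gives no figure for this point, so there is nothing to reproduce. The check is a comparison of the two readings, followed by rough sizing.

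**Reading 1: any post-baseline evaluation counts.** Blood pressure and pulse during and after the first infusion already qualify, so about 0 dosed patients are excluded. The week-12 tag then does nothing.

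**Reading 2: the week-12 tag is applied.** Three groups cannot have a week-12 evaluation or are unlikely to:

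- patients who have died;
- patients who have withdrawn consent (Protocol 3.3: "No further data will be collected on subjects once consent has been withdrawn");
- patients lost to follow-up with no later safety contact.

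Patients who only stop treatment early would generally stay in. Appendices 2 and 3 schedule safety visits counted from the last dose. With C1D1 as day 1:

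| Last dose | Follow-up visit | Study day | Week (with window) |
|---|---|---|---|
| C1, day 1 | +3 months | 92 | 13.0 (12.0–14.0) |
| C2, day 29 | +2 months | 90 | 12.7 (11.7–13.7) |
| C3, day 57 | +30 days | 87 | 12.3 (11.9–12.7) |

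**Deaths before week 12 in cohort 4.** Inputs from Protocol 11.3: n = 33, and nine-month survival S9 of 13% (reference) or 13% + 10% = 23% (expected). Week 12 is t = 84/30.4375 = 2.76 months.

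- Constant hazard (assumption): S(t) = S9^(t/9).
  - S9 = 0.13: S = 0.13^(2.76/9) = 0.535; deaths = 33 × (1 − 0.535) = 15.3.
  - S9 = 0.23: S = 0.23^(2.76/9) = 0.637; deaths = 33 × (1 − 0.637) = 12.0.
- Hazard rising steeply from entry (Weibull, shape 4, assumption): S(t) = S9^((t/9)^4), giving 0.6 and 0.4 deaths.

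The constant-hazard figures ignore inclusion criterion 8 ("Life expectancy of at least 12 weeks"). If that criterion is effective, the count is near 0. These are deaths from any cause. The documents give no survival figure for cohorts 1 to 3.

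**Losses.** The sample size allows 31 − 28 = 3 in each of cohorts 1 to 3 and 33 − 30 = 3 in cohort 4, so 12 of 126. Spread evenly over nine months (assumption), 12 × 2.76/9 = 3.7 fall before week 12. The possible range is 0 to 12.

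**Effect of one excluded toxic death in cohort 4 (illustration).** All dosed patients: 1/33 = 3.0%, Clopper-Pearson 95% CI 0.1–15.8%. With that patient outside the set: 0/32 = 0%, CI 0–10.9%.

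**The case against.** The wording itself leans towards the harmless reading. Asking for at least one evaluation makes little sense if only one time point can qualify, and the tag looks carried over from the tumor-assessment bullet. That explanation does not fit everywhere, since SAP 3.5 and SAP Table 1 schedule scans every 8 weeks for the first 48 weeks. The synopsis says fatal adverse events will be among those analyzed, which also points away from dropping them. Both arguments bear on intent, but neither redefines the set.

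An early toxic death would not disappear from the record. It would be reported as a serious adverse event (Protocol 10.3.2.1), the patient would be named in SAP Table 4, SAP 3.7.8 calls for data listings, and overall survival uses the Full Analysis Set. Some patients who stop attending would still be reached by phone or mail (Protocol 3.3 and 4.3). The safety table shells name no analysis set, so the link to every table rests on the general statements in Protocol 11.1 and 11.2 and SAP 3.7.1 and 3.7.3. Those statements are explicit. These safeguards limit the harm, but they do not restore the toxicity rates.

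The sizing is also soft. The upper death count needs a constant hazard and disregards an entry criterion, the lower one uses an assumed shape, and deaths clearly due to progression are not toxicity events. That argues for restraint on severity and leaves the point about the definition intact.

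Finally, deleting only the week-12 tag would remove the ambiguity. It would still leave a condition that a dosed patient with no recorded evaluation fails, and that condition serves no purpose.

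**Conclusion.** The concern holds in its conditional form. The only safety set carries a condition with two readings, and the documents do not choose between them. Under the first, about 0 patients are excluded. Under the second, membership depends on surviving and staying to week 12, and the number excluded cannot be derived: near 0 to about 15 deaths in cohort 4 on the stated hazard assumptions, plus about 3.7 losses across 126 patients (range 0 to 12) if losses are spread evenly. The direction of the bias for fatal toxicity is clear, because an early toxic death can only be removed.

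This should be fixed. Confidence is medium, because the intended meaning of the tag is unknown; the text of the definition is not in doubt.

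**What to change.** In Protocol 11.1, SAP 3.7.1 and SAP Table 3, define the Safety Analysis Set as all patients who received at least one dose of durvalumab or tremelimumab, and delete the whole post-baseline evaluation condition along with its week-12 tag. If every allocated patient is dosed, the denominators are 31, 31, 31 and 33.

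As an optional presentation change, add a Grade 5 row to SAP Tables 112 and 117, which stop at Grade 4. Tables 113 to 115 already cover grade 3 and above.

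The cost is one clause deleted in three places, with no new data and no change to the design.
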